CONCLUSION. The team has extensive experience evaluating and transporting EBPs. Our research suggests that while family-based CM is a well-validated EBP for adolescent SUD, its effects, like other adolescent SUD EBPs, are modest. Thus, this study will use an experimental mediation approach to identify mediating processes in treatment, with the ultimate aim of improving SUD treatment effectiveness. Backed by our experience conducting mediation and clinical studies, this study is poised to produce crosscutting implications for improving youth SUD treatments. Given the clear need to enhance effectiveness and durability of existing interventions, such work could have a dramatic impact on outcomes and services for youth.

DESIGN TIMELINE AND OVERVIEW

Data will be from a Ionaitudinal twoarmed parallel group design with 172 youth randomized to CM vs. CM+. In-person assessments will be at baseline, 2-, 4-, 6-, 9-, and 12-months postbaseline. Phone assessments will be at 1-, 3-, 5-, 7-, and 8months post-baseline.

STUDY SITES

The proposed study will be conducted with the OSLC outpatient clinic and Centro Latino Americano (CLA). Both are Medicaid-approved, HIPAA-compliant clinics employing Certified Alcohol and Drug Counselors (CADC) to deliver treatment services. While the two clinics serve all Lane County residents, CLA clients are predominantly Latino. As noted in the *Introduction*, adding CLA as a second site for this trial allows for oversampling of Latino youth, permitting an examination of differential mediation effects by ethnicity (see *Data Analysis*). Importantly, OSLC scientists regularly collaborate with OSLC clinic staff on intervention trials involving methods consistent with the proposed study. Similarly, OSLC scientists have a long history of collaborating with CLA on research and implementation projects. 149-150 Thus, the sites are optimal for ensuring adequate recruitment numbers, protocol fidelity, and successful completion of study procedures.

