RECRUITMENT AND RETENTION RATES. In over 15 years conducting treatment research with families, we have achieved recruitment rates ranging from 85-100% and retention rates exceeding 90% for 12-month follow-ups. 34,55,107 The research team has been very successful at recruiting and retaining participants from challenging populations, and the majority of these studies were conducted in real world (rather than research) clinics where youth/families could receive treatment without consenting to research. We will replicate our successful recruitment and retention strategies in this trial. First, to establish collaborative relations with families, assessments are scheduled at their convenience, contacts are as friendly as possible, and families are reimbursed for their time. Second, direct contact helps maintain the cohort, with families contacted regularly during their 12 months of study participation. At each contact, families are asked if they plan to move and for up to 4 phone numbers and email addresses of best friends, relatives, and schools/places of employment. Third, we obtain consent to use technology such as text messaging and Facebook (using private messaging functions). When participants cannot be located, Assessors track them using the various contacts, other Internet resources (e.g., reverse look-up), and post office forwarding. Fourth, the same Assessor follows participants over time to encourage rapport. Fifth, contacts are defined as confidential and independent of treatment. Reasons for missed interviews will be recorded to assess impact on proposed methods.

RANDOMIZATION TO CONDITIONS

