b-path. This model is more complex, simultaneously evaluating the mediator and outcome processes. To obtain this coefficient, the a-path is modeled along with the outcome model (c-path; testing for differences between CM+ and CM on substance use and externalizing behavior). With fewer outcome measurements, the model includes a during-treatment slope term and indicators to differentiate 9- and 12-month assessments, providing three estimates: during-treatment slope, change at 9 months, and change at 12 months. To obtain the b-path coefficient, a regression is specified with *during-treatment mediator slope* as a predictor of *outcome at 9 and 12 months*. This provides a targeted test of mediation, with during-treatment change in the mediator as a predictor of post-treatment outcomes.

Ethnicity effects. In close consultation with project consultant [name], and to address potential for differential effects across project clinics, formal moderated mediation tests can be performed.²⁰⁸⁻²⁰⁹ These tests determine whether observed mediation effects differ for Latino and non-Latino youth/parents. Sample size means that results are hypothesis-generating and thus will focus on estimation of confidence intervals. The same approach will be used to evaluate moderated mediation for ethnicity in Aims 2 and 3.

Confounding variables. Although randomization, the enhancement mediation design, and models addressing temporal sequencing increase the likelihood of valid causal inferences for mediation, a remaining assumption is that there are no unmeasured confounding variables for the mediator's effect. Cox et al.²¹⁰ recommends sensitivity analyses for confounder bias be used. First, VanderWeele's²¹¹ formulas identify youth/parents with the same value on the mediator but different values on the outcome, as well as youth/parents with the same value on the mediator across both CM and CM+ groups. Second, residuals from the models just detailed should be uncorrelated, and Mplus code from Imai et al.²¹² is used to determine whether the mediated effect differs based on unmeasured pre-treatment variables. Third, Mauro's²¹³ correlational method evaluates the sources of error variance from the mediation model, determining how large the effect of an omitted variable

would need to be to negate the mediated effect.

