STATISTICAL POWER FOR MEDIATED EFFECTS. The proposed mediation models include estimates of: (1) the effect of the initial variable on the hypothesized mediator (α-path), (2) the effect of the hypothesized mediator on the outcome (β-path), and (3) the mediated effect (αβ). Using Monte Carlo simulations implemented in Mplus, $^{214-215}$ power is determined by the percentage of replications with a significant effect for the path of interest. Using covariance algebra provided by Thoemmes et al., 215 parameters (path coefficients, variances, residuals) were tailored to reflect α- and β-paths with small-to-medium ($R^2 = .07$) effects. For each model, sample size, conservatively assuming 10% attrition, was 155, with 10000 replications from the population. For a-path, power was >.90 to detect a small-to-medium effect of the initial variable on the mediator. For β-path, power was .85 to detect a small-to-medium effect of intermediate targets on ultimate outcomes. For the mediated effect, power was .83. This estimate is conservative due to the simulation's Sobell *SE* method. As an upper bound on power, and based on simulations using the proposed asymmetric *SE* method, Fritz and MacKinnon²¹⁶ found a sample of *N*=74 sufficient for .80 power to detect medium effects for α- and β-paths.

ATTRITION AND MISSING DATA

Participants will be retained in research measurement independent of CM/CM+ participation following intent-to-treat principles.²¹⁷ Along with this, the successful participant tracking and retention protocols used in OSLC research will minimize missing data. However, because some data will inevitably be missing, methods recommended by Schafer and Graham²¹⁸ will evaluate assumptions and guide analyses. Three steps will be used: (1) For a small proportion of missing data with evidence of Missing at Random (MAR), data will be analyzed using the estimation procedures described above. (2) For a non-trivial amount of missing data and evidence of MAR, multiple imputation for repeated measurements will generate complete data.²¹⁹ (3) For a non-random missing data mechanism, pattern mixture models will identify and control its effects.^{203–204}

BIBLIOGRAPHY & REFERENCES CITED

- 1. [name], P., & Reid J. (1987). Parent observation and report of child symptoms. *Behavioral Assessment*, 9, 97-109.

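### The not-at-random analysis depends on a judgement about MAR that observed data cannot settle; it should be run in every case, under stated assumptions.

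*Combined protocol and SAP*

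**What the plan says.** The rule stands in the combined protocol and SAP under Attrition and Missing Data. Methods from a cited paper on missing data "will evaluate assumptions and guide analyses", in three steps:

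- **Step 1** begins "For a small proportion of missing data with evidence of Missing at Random (MAR" and keeps the main estimation procedures.
- **Step 2**: "For a non-trivial amount of missing data and evidence of MAR, multiple imputation for repeated measurements will generate complete data".
- **Step 3**: "For a non-random missing data mechanism, pattern mixture models will identify and control its effects".

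No diagnostic or criterion for deciding between MAR and a non-random mechanism is written out. The boundary between a small and a non-trivial amount of missing data is not defined either.

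Two other places bear on the point. Under Recruitment and Retention Rates: "Reasons for missed interviews will be recorded to assess impact on proposed methods". Under Aim 1, on confounding variables, the plan notes that a cited paper "recommends sensitivity analyses for confounder bias be used". The sensitivity analyses described there concern confounding, not missing data.

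**The concern.** Steps 1 and 2 both assume MAR. Whether anything else is done depends on classifying the mechanism. MAR is a statement about values nobody has seen: given what was observed, the missing values behave like the observed ones. If missingness is related to earlier measurements, that is evidence against missing completely at random, but it is fully compatible with MAR. The trigger therefore asks the data for something they cannot give, and no not-at-random analysis is assured.

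The wording of step 3 adds to this. A pattern-mixture model shows the result under an assumption about how the unseen values differ. It does not discover that difference. The plan states no identifying restriction or range of shifts.

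What is at stake is the later visits. Under Aims 1 and 2 the b-path is a regression of 9- and 12-month levels on the during-treatment slope of parent management. Aim 3 uses post-treatment levels from the same outcome model. In a trial of adolescent substance use, current use is a plausible cause of a missed visit, so a departure from MAR at those visits cannot be dismissed beforehand.

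**Working it through.** **1. The plan's own figure.** The design has "172 youth randomized to CM vs. CM"+. On power, the plan says: "For each model, sample size, conservatively assuming 10% attrition, was 155". Check: 172 × (1 − 0.10) = 154.8, so 155. The figure reproduces, and nothing below disputes it.

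**2. The rule as a decision table.**

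| Amount missing | Mechanism judged | Method | Assumption |
|---|---|---|---|
| small (undefined) | MAR | main estimation | MAR |
| non-trivial (undefined) | MAR | multiple imputation | MAR |
| any | non-random | pattern mixture | not stated |

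The second column decides whether a not-at-random analysis is run, and the plan gives no criterion for it.

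**3. Can observed data fill the second column?** A simulation with N = 172 (from the plan) used two standardised measurements. The remaining inputs are assumptions, because the documents give none: correlation 0.5; dropout at the second measurement depending on the observed first value (logistic slope 0.5 per SD); overall missingness of 10% or 20%; and unseen values of dropouts shifted by δ = 0 (MAR), 0.5 or 1.0 SD. There were 4,000 replications per setting. The diagnostic was a t-test of the first value by missingness. The MAR estimate predicted missing values from the regression among those observed.

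| Missing | δ (SD) | Diagnostic rejects | Completer mean | Bias of MAR estimate (SD) |
|---|---|---|---|---|
| 10% | 0 | 46.8% | −0.024 | 0.00 |
| 10% | 0.5 | 48.0% | −0.022 | −0.05 |
| 10% | 1.0 | 48.3% | −0.024 | −0.10 |
| 20% | 0 | 73.2% | −0.048 | 0.00 |
| 20% | 0.5 | 72.1% | −0.048 | −0.10 |
| 20% | 1.0 | 72.6% | −0.047 | −0.20 |

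The diagnostic and the completer mean do not move with δ beyond simulation error. The standard error of each rejection rate is about √(0.47 × 0.53 / 4000) = 0.8 points at 10% missing. The bias does move, and equals −(missing fraction × δ). This follows from the construction: δ is added only to values that are never observed, so the observed data have the same distribution for every δ. Any diagnostic computed from the observed data would fail in the same way.

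**4. Illustrative size for the arm difference.** Suppose only one arm's dropouts carry a residual shift δ, meaning the part not predicted by their earlier data. Then:

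bias in arm difference = missing fraction × δ

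- 10% missing: 0.10 × 0.25 = 0.025 SD; 0.10 × 0.5 = 0.05 SD; 0.10 × 1.0 = 0.10 SD.
- Over 5% to 20% missing: from 0.05 × 0.25 = 0.0125 SD to 0.20 × 1.0 = 0.20 SD.

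As a yardstick, an unadjusted comparison at one visit with 155 / 2 = 77.5 per arm has a standard error of √(2 / 77.5) = 0.16 SD. At 10% missing the bias is therefore 0.025 / 0.16 ≈ 0.16 to 0.10 / 0.16 ≈ 0.6 of a standard error.

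**5. Does another section repair the rule?** The recorded reasons for missed interviews are not linked to the three steps. The Aim 1 sensitivity analyses address confounders. The citation does not supply the specification either: the superscript on the step 3 sentence is 203–204, which in the reference list are papers on coding of time and on confidence limits for indirect effects. The reference on random-effects pattern-mixture models is number 221.

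**The case against.** The strongest reply has four parts.

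- **The plan is not naive about missingness.** It names a not-at-random method and gives it a step of its own. It records why interviews were missed, which is information from outside the outcome data. A recorded reason such as relapse could lead an analyst to step 3. This stands in part: reasons can support a judgement of plausibility, but they cannot establish MAR, and the rule does not use them.
- **No formal test is named.** A reader might infer that the plan relies on a statistical test of MAR, or that the analyst will nearly always stop at step 1 or 2. The documents support neither. They speak of evidence and of evaluating assumptions, and how often step 3 would be reached is a prediction. The defect is that step 3 is conditional and has no criterion.
- **The arithmetic concerns the arm difference.** That is the c-path, which the plan calls preliminary, and mediation is tested whether or not it is significant. The b-path controls for treatment, so a shift confined to one arm's dropouts goes mainly to the direct effect. How much reaches the b-path depends on whether missingness is also related to the mediator. This stands. The repeated-measures model also uses earlier visits, so only the unpredicted part of any shift is bias. A figure built on completer urine-screen rates alone would be an upper bound.
- **Exposure is limited.** Measurement continues after treatment dropout, tracking is detailed, and past 12-month retention is given as above 90%. This also stands and keeps the likely effect modest.

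**Conclusion.** The concern holds as a fault in the decision rule. The choice between an MAR and a not-at-random analysis rests on a distinction that observed data cannot make, no other section mends it, and step 3 claims more than a pattern-mixture model can do without stated assumptions. It should be changed before analysis, because the remedy is a better method and not just added detail.

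The size is illustrative. With 10% missing and a residual shift of 0.25 to 1.0 SD in one arm's dropouts, the arm difference is biased by about 0.025 to 0.10 SD. The shifts are assumed; the documents give no value for them. Bias in the b-path and the mediated effect is not quantified here and may be smaller. A reader might go on to infer a particular inflation of the false-positive rate, or that the mediation results are invalid. Neither follows: the first needs a worked null scenario for the planned model, which the documents do not allow, and the second would need evidence of bias in the product of paths.

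**What to change.** Under Attrition and Missing Data:

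1. Delete the condition on evidence of MAR.
2. State the MAR likelihood analysis as primary, using all available data with auxiliary predictors of missingness. Allow multiple imputation under the same assumption as an equivalent option.
3. Always run a prespecified pattern-mixture or delta-adjusted sensitivity analysis over a stated range of shifts, by arm. Cover the 9- and 12-month outcomes in the b-paths: substance use and externalizing behavior, and the Aim 2 outcomes (behavioral regulation and peer relations).
4. Report how the mediated effect changes over that range.
5. Say that the recorded reasons for missed interviews will guide the range.
6. Replace the claim in step 3 with the identifying assumptions to be used, and correct its citation.

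Cost: a few sentences and several additional model runs, since there are several outcomes, two visits and a bootstrapped product. No new data are needed, and the sample size and power figures do not change.
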